9.0 Safety and Effectiveness Assessments

The primary goal of this pilot study is to determine if MRI with multiparametric sequences mpMRI can be used as a mapping tool for correlation with histopathology results, providing a more informed method for the delivery of focal hypofractionation treatments. Hypofractionated radiation using SBRT is a promising tool for delivery with intent to cure. The use of focal partial prostate SBRT should show lower toxicity, and will be evaluated for equivalent efficacy. A co-primary end point of the pilot study will be to show that patients maintain acceptable HRQOL status as compared to baseline. There will be two co-primary endpoints based on summary scores from the bowel and urinary domains of the EPIC questionnaire. Although HRQOL is collected at multiple time points, it has been decided that EPIC, EQ D5 and Sexual Medication/Device Screening data collected at 6, 12 and 24 months post therapy will be compared to baseline to test the primary hypothesis. The percentage of patients with change in EPIC bowel domain score (baseline to 1-year) that was worse than 5 points and a change in EPIC urinary domain score that was worse than 2 points are felt to be clinically meaningful endpoints to assess for tolerability and safety. A rate for the worse-than-5 point change in bowel score of up to 35% of patients will be considered acceptable, with a rate $\geq 55\%$ specified as unacceptable. Similarly, a rate for the worse-than-2 point change in urinary score of up to 40% will be considered acceptable, with a rate $\geq 60\%$ unacceptable. The PSA results along with serial MRI assessments will be used to test the hypothesis of equivalent disease control compared to historical data for whole gland therapy using SBRT. Standard of care quality of life assessments International Prostate Symptom Score (IPSS) and sexual health inventory for men (SHIM) scores will be acquired as part of the standard care prior to and following SBRT. When collected, this data will be collected and reported.

Analysis of the Primary Endpoints

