The disease-free survival duration will be measured from the date of treatment to the date of documentation of disease progression or until the date of death from any cause. DFS at 6, 12 and 24 months for each patient and the series by the Kaplan-Meier method (Kaplan 1958). Also, 95% confidence intervals will be reported.

Analysis for Endpoints Related to HRQOL

We will use three instruments to measure HRQOL: the Expanded Prostate Cancer Index Composite (EPIC), the Utilization of Sexual Medications/Devices, and EQ-5D. Protocol eligible patients will be included in the HRQOL analysis only if they have provided baseline and at least one subsequent measurement. All HRQOL instruments (EPIC, the Utilization of Sexual Medications/Devices and EQ-5D) will be collected on all cases participating in the trial. The standard departments QOL instruments may also be used to report outcomes with both the International Prostate Symptom Score (IPSS) and Sexual Health Information Measurement (SHIM) obtained from chart review.

The EPIC Supplement Utilization of Sexual Medications/Devices, and EQ-5D will be collected at pretreatment (baseline) and at 6, 12 and 24 months after radiation therapy ends. Patient self-assessment of symptoms will be performed using four primary EPIC scales: urinary, bowel, hormonal and sexual symptoms. The Utilization of Sexual Medications/Devices and EQ-5D Questionnaires are found in Appendix 3.

For all primary HRQOL analyses we will estimate the degree of change from baseline to 6, 12 and 24 months as continuous variables. For this endpoint, in each domain, the actual change score will be used as the statistic and a t-test will be used to evaluate if the change is different from 0. Confidence intervals also will be computed

The primary objective in HRQOL analysis is to estimate the change from baseline to 24 months. The response will be the change of measurement from baseline to 24 months (or the last available HRQOL data point where data are missing). The one-sample t-test will be used to test the null hypothesis that response change is 0. For the regimen to maintain the overall significance level for testing three HRQOL instruments. In addition, we will describe the distributions of HRQOL data collection patterns over all collection points in each treatment arm.

Demonstrate dosimetric and biological advantage of focal SBRT versus whole-gland therapy

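### The co-primary EPIC endpoints are worsening proportions with acceptability limits, but the primary HRQOL analysis is a t-test of mean change against 0, and no analysis is tied to the limits

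*Combined protocol and SAP*

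**What the plan says.** **Endpoints (section 9.0).** "There will be two co-primary endpoints based on summary scores from the bowel and urinary domains of the EPIC questionnaire". The bowel endpoint is "The percentage of patients with change in EPIC bowel domain score (baseline to 1-year) that was worse than 5 points". The urinary endpoint is the matching percentage for a drop of more than 2 points. Its phrase carries no time point; 1 year follows only by reading it in parallel with bowel. Limits are attached to both. For bowel, "A rate for the worse-than-5 point change in bowel score of up to 35% of patients will be considered acceptable", and 55% or more is unacceptable. For urinary, "a rate for the worse-than-2 point change in urinary score of up to 40% will be considered acceptable", and 60% or more is unacceptable. The same paragraph also says that HRQOL data "collected at 6, 12 and 24 months post therapy will be compared to baseline to test the primary hypothesis".

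**Analysis (section 9.1, HRQOL part).** "For all primary HRQOL analyses we will estimate the degree of change from baseline to 6, 12 and 24 months as continuous variables". Each change score is tested against 0 with a t-test. One time point is then singled out: "The primary objective in HRQOL analysis is to estimate the change from baseline to 24 months", with the last available value used where the 24-month value is missing. The test is given as: "The one-sample t-test will be used to test the null hypothesis that response change is 0".

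**Elsewhere.** The part of 9.0 on analysing the primary endpoints covers PSA, examination, MRI against biopsy, and RECIST; it does not mention EPIC. Section 10.2 names EPIC among the tools for evaluating toxicity and then says that side-effect and adverse-event rates will be given as proportions with 95% confidence intervals. For HRQOL it adds time-to-event reporting, repeated-measures ANOVA and mixed models. The four limits appear only in 9.0.

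**The concern.** Both sections use the word primary, so they cannot be reconciled as primary against secondary. Section 9.0 asks what share of men lose more than a stated number of points by about 1 year, and whether that share is tolerable. Section 9.1 asks whether the average change differs from 0, with 24 months first. A mean near 0 does not show that few men worsened, and a mean different from 0 does not show that too many did.

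An analyst who follows 9.1 would report a primary HRQOL result that does not address the declared co-primary endpoints and could point the other way. An analyst who follows 9.0 would find limits but no stated analysis, no meaning for results between them, and no rule for a man without a 12-month EPIC. With 12 men, settling these matters after the data are seen could change the tolerability conclusion.

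**Working it through.** **Inputs.** n = 12 (4.2; 10.2, Sample Size). Limits: bowel 35%/55%, urinary 40%/60% (9.0). Thresholds: more than 5 and more than 2 points (9.0). The plan gives no calculation on these limits, so there is no figure of its own to reproduce here.

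**1. The two definitions side by side.**

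| | Section 9.0 | Section 9.1 |
|---|---|---|
| Variable | share of men past a threshold | mean change score |
| Time point | 1 year (bowel); none stated (urinary) | 6, 12 and 24 months, 24 named as primary |
| Reference | 35%/55% and 40%/60% | 0 |

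**2. Can they disagree?** Constructed urinary example: 8 men change by -3 and 4 men by +6.
- Sum = 8 × (-3) + 4 × (+6) = -24 + 24 = 0, so the mean is 0, t = 0 and p = 1.
- Worse by more than 2 points: 8/12 = 66.7%, above the 60% limit.

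A bowel case works the same way: 7 × (-6) + 5 × (+8.4) = -42 + 42 = 0, with 7/12 = 58.3% worse by more than 5 points, above 55%.

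The reverse can also occur. Assume normal change scores and a two-sided 0.05 test (neither is stated in the plan). A true bowel rate of exactly 35% at SD 5 means a mean change of -3.07, and the t-test rejects no change 49% of the time. At SD 15 the mean is +0.78 and rejection is 5%. The documents give no SD, so only this range can be stated.

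**3. Limits read as observed rates, 12 evaluable men.**
- Bowel: 4/12 = 33.3% is acceptable; 5/12 = 41.7% and 6/12 = 50.0% lie between; 7/12 = 58.3% is unacceptable.
- Urinary: 4/12 = 33.3% is acceptable; 5/12 = 41.7%, 6/12 = 50.0% and 7/12 = 58.3% lie between; 8/12 = 66.7% is unacceptable.

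Probability of landing between the limits, with X binomial(12, p):
- Bowel, P(X ≤ 6) - P(X ≤ 4): at p = 0.35, 0.915 - 0.583 = 0.332; at p = 0.55, 0.473 - 0.112 = 0.361.
- Urinary, P(X ≤ 7) - P(X ≤ 4): at p = 0.40, 0.943 - 0.438 = 0.505; at p = 0.60, 0.562 - 0.057 = 0.505.

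**4. Would the 95% intervals of 10.2 settle it?** Exact (Clopper-Pearson) intervals, n = 12: 3 events, 5.5% to 57.2%; 4 events, 9.9% to 65.1%; 8 events, 34.9% to 90.1%. The interval covers both bowel limits at every count from 3 to 8 and both urinary limits from 4 to 8. Over that range the interval alone does not separate acceptable from unacceptable.

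**5. One man without a 12-month EPIC.** Four bowel events are 4/12 = 33.3% (acceptable) but 4/11 = 36.4% (above 35%). The denominator rule alone can change the result.

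**The case against.** **The proportions may already be covered.** A reader might infer that the plan never analyses EPIC as a proportion. The documents do not support that. Section 10.2 treats EPIC as a toxicity instrument immediately before it says rates are given as proportions with 95% intervals, and 9.0 presents the worsening percentages as tolerability and safety measures. Read together, the proportions could be reported. What stands is narrower: nothing links that reporting to the limits, and 9.1 still directs the primary test elsewhere.

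**It is a pilot.** The Sample Size text calls the study proof-of-principle, not powered for toxicity or QOL, and meant to supply preliminary data. This lowers the consequence, and the probabilities in step 3 mostly reflect n = 12. An inconclusive middle zone is also a legitimate design. But the plan does not say that the middle is inconclusive, and small size does not explain naming a different quantity as primary.

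**Missing data are not ignored.** Section 9.1 requires a baseline and one later measurement and carries the last value forward for the 24-month change; 10.2 assumes missing at random in mixed models; 5.1 allows replacement of withdrawn men. None of these says how a missing 12-month value counts in the proportion.

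**The binomial test in the Sample Size text.** A reader might take it as the test of the urinary limit, or try to refute its stated power with the 40% and 60% rates. Neither is supported. Its comparator is an unstated historical rate, so it neither fills the gap nor bears on this point.

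**The example is built to give mean 0.** True. It shows that the conflict is possible, not how likely it is.

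**Conclusion.** The contradiction is in the current text and should be fixed. The declared co-primary endpoints and the primary HRQOL analysis differ in variable, time point and null, and no analysis uses the 35/55% and 40/60% limits.

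If the limits apply to observed rates with 12 evaluable men, 5-6 events (bowel) and 5-7 events (urinary) have no stated meaning. That happens with probability 33-36% and about 50% respectively when the true rate sits at either limit. The mismatch itself needs no distributional assumption. The sizes assume 12 evaluable men and independent outcomes between men, and 1 year for the urinary endpoint is a parallel reading.

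A reader might go further and conclude that the trial will reach a wrong tolerability verdict, or that it must have a formal go/no-go test. The documents support neither: the extremes are decided by the limits as written, and a formal test is a debatable choice in a 12-man estimation pilot.

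**What to change.** In 9.0, 9.1 and 10.2, before outcome data are seen:

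1. Make the proportion worsening at 12 months the primary HRQOL analysis for each domain, and state the urinary time point explicitly.
2. Report each proportion with an exact confidence interval beside its limits.
3. State that the limits apply to the observed rate and that results between them are reported as inconclusive.
4. State the denominator rule for a man without a 12-month EPIC.
5. Relabel the 6-, 12- and 24-month mean-change t-tests as secondary estimates with confidence intervals.

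Optional, at the sponsor's choice: state a count per domain with its error rates. At most 4 of 12 is already what the observed-rate reading accepts in both domains. It gives false acceptance of P(X ≤ 4 | 0.55) = 11.2% for bowel and P(X ≤ 4 | 0.60) = 5.7% for urinary, and acceptance of 58% at a true 35% and 44% at a true 40%. The counts need restating if fewer than 12 men are evaluable.

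The cost is wording. EPIC is already scheduled at baseline and 12 months (4.3.10, 7.2, 7.3), so no new data are needed. The downside is that the wide uncertainty at n = 12 becomes explicit.

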9.2 Effectiveness Assessments

Clinical information from subjects will be recorded onto Case Report Forms and subsequently transferred into OnCore. Patients who additionally consent to a separate Urology Registry will have their data added to the Urologic Oncology & Minimally Invasive Therapies Database for UHHS Faculty.

Should any unanticipated adverse events occur during the course of the study, the clinical research coordinator will ensure that they are documented by the investigator and reported to the appropriate Institutional Review Board per its then-current guidelines. If the determination is made that an unanticipated adverse event presents an unreasonable risk to subjects, the clinical evaluation will be paused, or if deemed appropriate (to enable further investigation), the subject will be withdrawn as soon as safely possible.

Adverse events, grade 3 and above, will be captured in OnCore and will be reported in accordance with the Data and Safety Monitoring Plan (DSMP) that is approved by the Cancer Center Protocol Review and Monitoring Committee (and aligned with the NCI-approved plan).

Antitumor Effect – Solid Tumors

For the purposes of this study, subject PSA, DRE and PSA data will be recorded in Oncore as evaluations for response to radiation therapy, per standard of care procedure during post radiation therapy follow-up visits. In addition to PSA and DRE evaluations, RECIST (v.1.1) measurements will be acquired using mpMRI surveillance. Response and progression will be evaluated in this study using the new international criteria proposed by the revised Response Evaluation Criteria in Solid Tumors (RECIST) guideline (version 1.1) [Eur J Ca 45:228-247, 2009]. Changes in the largest diameter (unidimensional measurement) of the tumor lesions and the shortest diameter in the case of malignant lymph nodes are used in the RECIST criteria. We will also analyze volumetric response to therapy based on serial MRI data that will be evaluated using radiation oncology treatment planning computers.

Definitions

Evaluable for toxicity All patients will be evaluable for acute toxicity within 90 days from the time of the end of the course of radiation therapy.

Evaluable for objective response

Evaluable Non-Target Disease Response Patients who have lesions present at baseline that are evaluable, but do not meet the definitions of measurable disease, have completed a course of SBRT, and have had their disease re-evaluated by imaging will be considered evaluable for non-target disease. The response assessment is based on the presence, absence, or unequivocal progression of the lesions.

Disease Parameters

Radiologic Surveillance

Standard of care follow-up post RT will include contrast enhanced MRI and parametric imaging unless clinically contraindicated should include contrast.

Measurement of Response

Measurement of Response Prior to Study Entry

The revised RECIST guideline, v. 1.1. [European J of Cancer. 45: 228-247, 2009] will be used as applicable to the protocol. See

http://ctep.info.nih.gov/protocolDevelopment/docs/recist_guideline.pdf for further details.

Additional definitions beyond the RECIST guidelines specific to this protocol are incorporated to define local control as described below (Eisenhauer 2009). We will evaluate and report RECIST measures minimally at 12 and 24 months post radiation therapy.

Response Criteria: Evaluation of Target Lesions

Complete Response (CR): Disappearance of all target lesions

Partial Response (PR): At least a 30% decrease in the sum of the diameters of target lesions taking as reference the baseline sum diameters

Progressive Disease (PD): At least a 20% increase in the sum of diameters of target lesions, taking as reference the smallest sum on study (includes the baseline sum if that is the smallest on study). The sum must also demonstrate an absolute increase of at least 5 mm. The appearance of new lesion(s).

Stable Disease (SD): Neither sufficient shrinkage to qualify for PR nor sufficient increase to qualify for PD, taking the smallest sum diameters as reference while on study.

3D Lesion Volumes

In addition to RECIST criteria evaluation on follow-up scans, we will report 3 D volumetric data of individual lesions based on pre and post treatment images over time, for comparison to 2 D RECIST measurements (Guio 2012 and Eisenhauer 2009).

Measurable Disease Measurable lesions are defined as those that can be accurately measured in at least one dimension (longest diameter for non-nodal lesions and short axis for nodal lesions to be recorded) as ≥ 20 mm by chest x-ray, as ≥ 10 mm with CT scan, or ≥ 10 mm with calipers by clinical exam. All tumor measurements must be recorded in millimeters (or decimal fractions of centimeters).

Non-measurable disease All other lesions (or sites of disease), including small lesions (< 5 mm longest diameter) will be considered non-measurable disease. The presence of lymph nodes suspicious for metastatic disease during screening will be defined as an ineligibility criterion.

Target lesions Only a single target lesion which is biopsy positive will be selected for focal therapy and identified as the dominant target lesion and recorded and measured at baseline. Target lesion should be selected on the basis of size (lesions with the longest diameter). We will use T2 weighted MRI image sets with contrast for the baseline measurement.

Non-target lesions All other suspicious lesions should be identified as non-target lesions and should also be recorded at baseline. Measurements of these lesions are not required, but the presence, absence, or in rare cases unequivocal progression of each should be noted throughout follow-up.

Methods for Evaluation of Measurable Disease

All measurements should be taken and recorded in metric notation using a ruler or calipers. All baseline evaluations should be performed as closely as possible to the beginning of treatment. The same method of assessment and technique should be used to characterize the dominant lesion at baseline and during follow-up. Use of 3T MRI T2 scans with contrast is required for the baseline measurement and is the preferred method and technique for all imaging-based evaluations. The mpMRI image data will additionally be recorded, evaluated and reported separately.

Response Criteria

Evaluation of Target lesions

Response	Evaluation of Target Lesions
Complete Response (CR)	Disappearance of all target lesions. Any pathological lymph nodes (whether target or non-target) must have reduction in short axis to < 10 mm.
Partial Response (PR)	At least a 30% decrease in the sum of diameters of target lesions, taking as reference the baseline sum of diameters.
Progressive Disease (PD)	At least a 20% increase in the sum of diameters of target lesions, taking as reference the smallest sum on study (this includes the baseline sum if that is the smallest on study). In addition to the

	relative increase of 20%, the sum must also demonstrate an absolute increase of at least 5 mm. Note: the appearance of one or more new lesions is also considered progression.
Stable Disease (SD)	Neither sufficient shrinkage to qualify for PR nor sufficient increase to qualify for PD, taking as reference the smallest sum diameters while on study.

Evaluation of Non-Target lesions less than 5mm and /or detected on screening biopsy to involve less than 5% of the submitted tissue for carcinoma.

Response	Evaluation of Non-Target Lesions
Complete Response (CR)	Disappearance of all non-target lesions and normalization of tumor marker level. All lymph nodes must be non-pathological in size (< 10 mm short axis). Note: If tumor markers are initially above the upper normal limit, they must normalize for a patient to be considered in complete clinical response.
Non-CR/ Non-PD [Incomplete response/ Stable Disease (SD)]	Persistence of one or more non-target lesion(s) and/or maintenance of tumor marker level above the normal limits.
Progressive Disease (PD)	Appearance of one or more new lesions and/or unequivocal progression of existing non-target lesions. Unequivocal progression should not normally trump target lesion status. It must be representative of overall disease status change, not a single lesion increase. Although a clear progression of 'non-target' lesions only is exceptional, the opinion of the treating physician should prevail in such circumstances, and the progression status should be confirmed at a later time by the review panel (or Principal Investigator).

Evaluation of Best Overall Response

The best overall response is the best response recorded from the start of the treatment until disease progression/recurrence (taking as reference for progressive disease the smallest measurements recorded since the treatment started). The patient's best response assignment will depend on the achievement of both measurement and confirmation criteria.

For Patients with Measurable Disease (i.e., Target Disease)

Target lesions	Non-Target Lesions	New Lesions	Overall Response	Best Overall Response when Confirmation is Required*
CR	CR	No	CR	\geq 4 wks. Confirmation **
CR	Non-CR/Non-PD	No	PR	\geq 4 wks. Confirmation **

CR	Not evaluated	No	PR		
PR	Non-CR/Non-PD/not evaluated	No	PR		
SD	Non-CR/Non-PD/not evaluated	No	SD	Documented at least once ≥ 4 wks from baseline **	
PD	Any	Yes or No	PD	No prior SD, PR or CR	
Any	PD ***	Yes or No	PD		
Any	Any	Yes	PD		

* See RECIST manuscript for further details on what is evidence of a new lesion.
 
** Only for non-randomized trials with response as primary endpoint.
 
*** In exceptional circumstances, unequivocal progression in non-target lesions may be accepted as disease progression.
					

Note: Patients with a global deterioration of health status requiring discontinuation of treatment without objective evidence of disease progression at that time should be reported as “symptomatic deterioration.” Every effort should be made to document the objective progression even after discontinuation of treatment.
					

For Patients with Non-Measurable Disease (i.e., Non-Target Disease)

Non-Target Lesion	New Lesions	Overall Response
CR	No	CR
Non-CR/non-PD	No	Non-CR/non-PD *
Not all evaluated	No	Not evaluated
Unequivocal PD	Yes or No	PD
Any	Yes	PD

* ‘Non-CR/non-PD’ is preferred over ‘stable disease’ for non-target disease since SD is increasingly used as an endpoint for assessment of efficacy in some trials so to assign this category when no lesions can be measured is not advised.

RECIST (Eisenhauer 2009) Tumor Response

Tumor measurements will be defined by the PI or treating physician, and confirmed by an objective radiation oncologist or radiologist not associated with this study.

Duration of overall response: The duration of overall response is measured from the time measurement criteria are met for stable disease (SD), partial response (PR) or complete response (CR) - whichever is first recorded, until the first date that recurrent or progressive disease is objectively documented (taking as reference for progressive disease the smallest measurements recorded since the treatment started)

The duration of overall CR is measured from the time measurement criteria are first met for CR until the first date that progressive disease is objectively documented. CR will be reported as unconfirmed CR until a repeat image shows duration of response.

Duration of stable disease: Stable disease is measured from the start of the treatment until the criteria for progression are met, taking as reference the smallest measurements recorded since the treatment started, including the baseline measurements.

Biochemical Disease-Free Survival: The absence of PSA Clinical Nadir plus 2 ng/mL (Phoenix, Abramowitz (2007)).

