This protocol will require treatments to be performed with an image-guided technique with the use of a 3-D coordinate system defined by 3D sub-volume/s of the prostate using VMAT by the Synergy S Agility collimator (Elekta, Stockholm, Sweden and Atlanta, GA). A computerized method for image registration is required for determination of the patient shift information. Serial MRI images with parametric sequencing will be used both to evaluate intra fraction response and post therapy response. The intrafraction image (between the second and third fraction) will be evaluated for yield in intra-therapy response, that may be useful future in clinical applications such as in MRI-Linac based adaptive radiotherapy planning. Post therapy serial MRI will also be used to evaluate radiographic determined response to therapy, versus pre and mid treatment scans and as compared to clinical features such as PSA follow-up.

All available image sets will be co-registered using clinical software such as MIM Maestro (MIM software, Cleveland, OH) and PercuNav (Invivo, Gainsville, FL) and/or evaluated using our available in-house developed software for image registration verification, as is customary for clinical cases. Imaging data will thus be transferred to our Linac based treatment planning system Pinnacle, Philips Medical Systems (Cleveland, OH) for SBRT delivery. We will also use 3D cone-beam kV CT for alignment of *in-vivo* fiducials to track and adjust for internal target motion detection.

As previously described (6.1 Description of Radiation Therapy) a minimum of three and maximum of five radio-opaque fiducial markers will be inserted in to the prostate for use in fractionated dose target positioning during SBRT (delivered in three fractionated doses on 3 different days, typically every other day). At least one fiducial marker for treatment planning will be guided to a prostatic region reported on mpMRI to be highly suspicious for tumor burden.

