Treatment efficacy will be analyzed through PSA response, clinical exam, with the addition of serial MRI evaluations. Confirmation of multiparametric MR targets for focal SBRT with image guided biopsy, histopathology and fiducial marker position tracking will be evaluated for reporting accuracy of multiparametric and standard MRI sequences to detect disease. Prostate MRI including T2-weighted, contrast-enhanced, and diffusion weighted imaging along with computer aided detection (CAD) may be used to identify suspicious lesions for targeted biopsy and fiducial placement. Chi-square and cluster analysis will be used to correlate degree of suspicion on MR pulse sequences with incidence of cancer detected on biopsy and subsequently targeted for focal therapy. Post therapy MRI will be used to report response to therapy as either complete, partial, stable or progressive by RECIST criteria.

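### A tumour-marker condition in the non-target response table can turn a lesion that has gone on MRI into an overall partial response, against the plan's own lesion-based reading of MRI response

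*Combined protocol and SAP*

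**What the plan says.** **How MRI response is described**

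- Section 9.0, Analysis of the Primary Endpoints: "Post therapy MRI will be used to report response to therapy as either complete, partial, stable or progressive by RECIST criteria".
- Section 9.2, target lesions: "Complete Response (CR): Disappearance of all target lesions". There is no marker condition. One lesion per man is the target: "Only a single target lesion which is biopsy positive will be selected for focal therapy".
- Section 9.2, Evaluable Non-Target Disease Response: response is judged by whether the lesions are present, absent or have unequivocally progressed. No marker is mentioned.

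**Where a marker enters**

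- Section 9.2, non-target table, CR row: "Disappearance of all non-target lesions and normalization of tumor marker level", with the note "If tumor markers are initially above the upper normal limit, they must normalize for a patient to be considered in complete clinical response".
- Same table, Non-CR/Non-PD row: "Persistence of one or more non-target lesion(s) and/or maintenance of tumor marker level above the normal limits".
- Section 9.2, overall-response table (target, non-target, new lesions, overall): "CR Non-CR/Non-PD No PR".

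**How PSA is used elsewhere**

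- Sections 7.2, 9.1, 9.2 (Biochemical Disease-Free Survival) and 10.2 judge PSA by a rise of 2 ng/mL over the post-treatment nadir.
- Section 6.1.1 plans to look at serial MRI response "as compared to clinical features such as PSA follow-up".

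**The concern.** The non-target table puts a blood test inside a category that the plan otherwise presents as an imaging result. A man whose treated lesion has disappeared on MRI could be reported as an overall partial response because his marker stayed above normal, with nothing on the scan to support the lower category.

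Three features of this trial make that awkward. The rule needs an upper normal limit that the plan does not give. The treatment is focal and meant to spare non-cancerous prostate tissue (Section 1.2), so a limit applied to the whole patient does not measure the treated lesion alone. And MRI response is to be set against PSA: if PSA already helps decide the MRI category, some of the agreement between the two comes from the definition.

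**Working it through.** The plan states no CR rate, PSA normalisation rate or PSA upper normal limit, so there is no figure to reproduce. The check is of the text, followed by an illustration on assumed inputs.

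**1. Route from marker to category.** The Non-CR/Non-PD row joins its two conditions with and/or, so a raised marker is enough without any persisting lesion. The overall table combines target CR with Non-CR/Non-PD to give PR. The table for non-measurable disease carries non-target status straight into the overall response, so the same clause would deny CR there too.

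**2. Conflict.** The Section 9.2 definition of non-target response uses lesions only; the non-target table in the same section uses lesions and a marker. Section 9.0 says MRI is what reports the four categories. These statements cannot all govern the same result.

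**3. Which marker.** The table does not name it. PSA is the only tumour marker scheduled after treatment (Sections 7.2 and 7.3), and Section 9.2 records it as an evaluation of response. Reading the marker as PSA is therefore a reasonable inference. Eligibility caps PSA at 10 ng/mL but gives no normal limit. For example, suppose the lesion disappears and PSA falls from 8 to a stable 5 ng/mL. If the limit is below 5, the man has target-lesion CR, overall PR and no biochemical failure. If the limit is 5 or higher, the clause does not downgrade him.

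**4. Effect per man.** With 12 patients, one reclassification moves the CR rate by 1/12 = 8.3 percentage points.

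**5. Illustration (all rates assumed).** Let c be the target-lesion CR rate, e the share of men above the limit at entry, and m the share of those who normalise. Assume that the note applies to every such man, that lesion response is independent of PSA, and that nothing else lowers the category.

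- Marker condition met: q = 1 − e(1 − m)
- Overall CR: o = c × q
- Expected CRs turned into PR: 12 × c × (1 − q)
- Correlation of overall CR with the marker condition: phi = o(1 − q) / √[o(1 − o)q(1 − q)]

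With c = 0.70, lesion-only scoring gives 12 × 0.70 = 8.4 expected CRs. With the marker clause:

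| e | m | q | Overall CR of 12 | CR turned into PR | phi |
|---|---|---|---|---|---|
| 0.25 | 0.9 | 0.975 | 8.2 | 0.2 | 0.23 |
| 0.5 | 0.5 | 0.75 | 6.3 | 2.1 | 0.61 |
| 1 | 0.1 | 0.10 | 0.8 | 7.6 | 0.82 |

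If no man starts above the limit (e = 0), nothing changes. The phi values arise although lesion response was set independent of PSA: a man whose raised marker does not normalise cannot be an overall CR by definition. For target-lesion response or 3D volume, which contain no marker, the built-in association is zero.

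**The case against.** The case for leaving this alone has several sound parts.

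- **Different levels.** Target CR with a lower overall category is how the overall table is meant to work, so target CR and overall PR in one man are not rival definitions. This stands. The conflict lies instead between the lesion-only definition of non-target response and the marker clause in the non-target table.
- **Unclear reach.** The non-target table is headed for small or low-volume lesions, and the overall table has no row for a man with no non-target lesions. His route to a downgrade is not shown. But the note is worded for the patient, not the lesion, so the reach is ambiguous rather than nil.
- **Circularity.** A reader might infer that the MRI–PSA comparison is circular. The documents do not support that as it stands. Section 6.1.1 speaks of radiographic response and does not name the overall category. Section 9.2 obtains RECIST measurements in addition to PSA and also reports 3D lesion volume; Section 10.2 tests tumour volume before and after treatment. The dependence exists only if the overall category is used, and the plan does not say whether it is.
- **Untreated gland.** A reader might also infer that most of the PSA-producing gland is left untreated, so that PSA will often stay raised. The documents give no treated share and do not say that spared tissue keeps PSA up. They support only that part of the gland is spared.
- **Limited consequence.** RECIST findings are to be reported descriptively (Section 10.2), with no target CR rate or decision rule, and RECIST is adopted only so far as it applies to the protocol. That limits the weight of the point and also leaves room for the correction.

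**Conclusion.** The point holds as a conflict between stated rules. Followed as written, the plan can change a reported overall response from CR to PR on a blood test, while it says elsewhere that MRI and the lesions decide. It rests on two readings: that the unnamed marker is PSA, and that the note applies to the man concerned.

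The size is unknown. Only men above an unstated limit at entry who also reach target-lesion CR can be affected, and there may be none. The illustrated range of 0.2 to 7.6 men of 12 reflects the assumed rates and is not an estimate. It would go too far to conclude that complete responses in general are downgraded: target-lesion CR carries no marker condition.

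The EPIC and toxicity endpoints are not affected. Nor are the progression criteria, which contain no marker term. What is exposed is the descriptive overall CR/PR split and, if the overall category is chosen, the comparison of MRI response with PSA.

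**What to change.** - In Section 9.2, remove the marker condition and its note from the non-target CR and Non-CR/Non-PD rows for imaging response, so that MRI response is scored from lesions alone.
- In Sections 6.1.1 and 9.0, state that this imaging-only category is the one reported as MRI response and compared with PSA.
- Keep PSA as its separate nadir +2 ng/mL endpoint, and cross-tabulate it with imaging response.

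The change is to wording only and needs no extra data. Its cost is a small departure from the generic RECIST table. If comparability with that table is wanted, report the marker-inclusive overall category as a secondary description, with the marker and its upper normal limit named.
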